6.1 Handling of Missing or Incomplete Dates for Adverse Events and Concomitant Medications

Adverse Events

Handling of partial dates is only considered for the start date. An adverse event with a partial start date is considered treatment emergent if:

- only the day is missing and the start month/year is the same or after the month/year of the first dose
- the day and month are missing and the start year is the same or greater than the year of the first dose date
- the start date is completely missing

Concomitant Medications

Handling of partial dates is only considered for the stop date. A medication with a partial stop date is considered concomitant if:

- only the day is missing and the stop month/year is the same or after the month/year of the first dose
- the day and month are missing and the stop year is the same or greater than the year of the first dose date
- the stop date is completely missing or the medication is ongoing

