2.2 Safety

Safety of the test and reference products will be compared by evaluating the nature, severity and frequency of their adverse event profiles. All adverse events that occur during the study (from the moment a subject signs an informed consent) will be recorded. Descriptions of reactions or complaints will include the approximate date of onset, the date the adverse event ended, the severity of the adverse event, and the outcome. Comparisons between the

treatment groups will be made by tabulating the frequency of subjects with one or more adverse events (classified into MedDRA terms) during the study. Pearson's Chi-Square test or Fisher's Exact test, whichever is most appropriate, will be used to compare the proportion of subjects in the two active treatment groups with any adverse event. [REDACTED]

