5. PROCEDURES

5.1 Subject Screening and Enrollment

The study personnel will review the IRB approved informed consent form and assent form, if applicable, with each subject and give the subject an opportunity to have all questions answered before proceeding. The consent/assent form must be signed by each subject and witnessed before the subject is enrolled into the study. A copy of the signed consent/assent will be given to every participant and the original will be maintained with the participant's records. Subjects under the legal age of consent must sign an IRB approved written informed consent/assent in addition to a parent or legally authorized representative.

Subjects that require a wash-out [REDACTED] from their initial informed consent signing must be re-consented before any further study procedures can begin.

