7.3 Eliciting and Reporting of Adverse Events

The investigator will periodically assess subjects for the occurrence of adverse events. In order to avoid bias in eliciting adverse events, the subject or parent/legally authorized representative should be asked a non-specific question (e.g., "How have you been feeling since your last visit?") to assess whether any AE has been experienced since the last visit. All adverse events (as defined in Section 7.2), either observed by the Investigator or one of his/her medical collaborators, or reported by the participant spontaneously, or in response to direct questioning, will be reported and documented in the source and the study reporting forms. When reporting an adverse event, the Investigator must assign a severity grade to each event and declare an opinion on the relatedness of the event to the study medication or procedure. Serious or unexpected adverse events must be reported to Perrigo **within 24 hours** of when the Investigator first learns of the occurrence of the event.

Adverse events will be documented in source and recorded in a timely manner on eCRFs. Adverse events (i.e., worsening of Actinic Keratosis*) that are identified at the last assessment visit (or the early termination visit), must be recorded on the AE eCRF with the status of the AE noted.

* Worsening of the subject's Actinic Keratosis may be expected from application of the study medication. Therefore, this will only be identified as an adverse event if alternative treatment is required.

Adverse event reporting begins from the signing of informed consent/assent. Worsening of Actinic Keratosis from baseline will be considered a new adverse event and will be documented on the source document and eCRFs. Adverse events should be followed until resolved or 30 days after the final study treatment. In any case, serious adverse events that are not resolved or considered to be chronic within 30 days of the final study treatment must be followed by the investigator until they become resolved or are considered to be chronic (stabilized for at least 30 days). All events that are ongoing at this time will be recorded as ongoing on the eCRF.

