5.6 Safety Variables and Analyses

Duration of Treatment and Medication Compliance

Number of applications, days of exposure, and compliance rate will be summarized by treatment group using descriptive statistics. For each subject, the overall duration of treatment (days) will be calculated using the following formula:

$$(\text{Date of last application of study medication}) - (\text{Date of first application of study medication}) + 1.$$

Medication compliance rate (%) will be calculated for each subject as follows:

$$(\text{Total number of applications used}) / (\text{Expected number of applications}) * 100\%.$$

Subjects who complete the study are expected to have 3 applications. Subjects will only be considered compliant if they apply all three daily doses on study Days 1-3. For prematurely discontinued subjects, expected number of applications will be determined based on the overall duration of treatment by the time of discontinuation. Descriptive summaries of exposure and medication compliance rate will be provided by treatment group for the ITT subjects

Adverse Events

Adverse events (AEs) will be coded in MedDRA, version 15.1. Treatment-Emergent Adverse Event (TEAE) is defined as any AE occurs on or after applying the first dose of study drug. Number and percent of subjects reporting TEAEs will be tabulated by treatment group. Summaries will be presented by body system and preferred term for the ITT population, and further by severity and relationship to study medication. [REDACTED]

[REDACTED] In the summaries of incidence rates (frequencies and percentages), severity and relationship to study drug, subjects who report more than one event that are mapped to the same preferred term will be counted only once under the strongest severity and relationship, accordingly Fisher's exact test will be used to compare the proportions of subjects of the two active treatment groups who report any TEAE.

Treatment-Emergent Serious Adverse Events (TESAEs) will be discussed within the clinical study report. TESAEs and TEAEs that led to treatment interruption or discontinuation will be presented in data listings.

Concomitant Medications

Concomitant medications will be coded using the WHO Drug Dictionary, version September 2014, and will be presented in data listings.

Application Site Reactions

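### An adverse event with an incomplete start date is counted as treatment emergent even when its recorded stop date is before the first dose

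*SAP*

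**What the plan says.** SAP 5.6 gives the definition: "Treatment-Emergent Adverse Event (TEAE) is defined as any AE occurs on or after applying the first dose of study drug".

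SAP 6.1 then deals with incomplete dates for adverse events. It opens with "Handling of partial dates is only considered for the start date" and treats an event as treatment emergent in any of three situations:

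- Start known to the month. The rule applies when "only the day is missing and the start month/year is the same or after the month/year of the first dose".
- Start known to the year alone. Here the event counts if that year is not earlier than the year of first dosing.
- No start information at all. When "the start date is completely missing", the event counts with no further condition.

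No rule refers to the date on which the event stopped. The protocol does collect it: section 2.2 lists "the date the adverse event ended" among the items recorded for each event.

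Events before the first dose can be on file. Protocol 7.3 states: "Adverse event reporting begins from the signing of informed consent/assent". Protocol 9 requires consent before a subject is withdrawn from current medication for the study, and Protocol 5.1 makes separate provision for "Subjects that require a wash-out".

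**The concern.** A definition and the rule that implements it should not give opposite answers for the same event. An event that has already stopped cannot occur on or after a later first dose, so under SAP 5.6 it is not a TEAE. Under SAP 6.1 it is one whenever its start date is incomplete in one of the three listed ways.

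The flag feeds the any-TEAE proportion, which SAP 5.6 compares between the two active arms with Fisher's exact test. That is the only between-active safety test in the visible SAP text. One such event moves a subject with no other TEAE from the unaffected to the affected group. The event also enters the incidence and severity tables.

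Events before dosing have nothing to do with the assigned product. Counting them tends to make the two active arms look more alike, which is not the cautious direction when the aim is to show comparable safety.

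**Working it through.** The plan states no figure to reproduce. The check applies the three SAP 6.1 rules as written to a set of date patterns, with complete start dates handled by the SAP 5.6 definition. It then repeats this with one added condition: not a TEAE if a complete stop date is before the first dose. The first dose is assumed to be on 20 June 2015; the date is only an illustration.

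| Start date recorded | Stop date | SAP as written | With stop-date condition |
|---|---|---|---|
| June 2015, day missing | 15 June 2015 | TEAE | not TEAE |
| 2015, day and month missing | 30 May 2015 | TEAE | not TEAE |
| wholly missing | 15 June 2015 | TEAE | not TEAE |
| May 2015, day missing | 15 June 2015 | not TEAE | not TEAE |
| 2014, day and month missing | 15 January 2015 | not TEAE | not TEAE |
| 10 June 2015, complete | 15 June 2015 | not TEAE | not TEAE |
| June 2015, day missing | 25 June 2015 | TEAE | TEAE |
| wholly missing | missing | TEAE | TEAE |

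The first three rows are the defect. The events ended 20 − 15 = 5 days, 1 + 20 = 21 days and again 5 days before the first dose, yet are counted as TEAEs. The next three rows are handled correctly already. In the last two the timing is unknown, and the default of counting the event is kept.

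The second row needs a gap of at least 21 days between consent and first dose. Whether a gap that long occurs cannot be checked, because the wash-out lengths are redacted.

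A partial stop date can also settle the question. With the same first dose, a stop date of May 2015 with the day missing is conclusive, because May precedes June. A stop date of June 2015 with the day missing is not, and the default applies.

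The direction of the effect on the any-TEAE comparison follows from simple algebra. Let P be the true proportion with any TEAE in an arm. Let f be the probability that a subject has a misclassified pre-dose event, assumed equal in both arms and independent of true TEAE status. The observed proportion is P + f(1 − P), so the observed difference is

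(P_T − P_R) × (1 − f).

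The documents give no value for f. Purely as an illustration, assume 20% of subjects need a wash-out, 10% of those have a pre-dose event and 10% of such events have a partial start date: 0.20 × 0.10 × 0.10 = 0.002. With 50%, 20% and 10%: 0.50 × 0.20 × 0.10 = 0.01. Both are before requiring a known stop date ahead of dosing, which lowers them. The difference would then be multiplied by no less than 1 − 0.002 = 0.998 or 1 − 0.01 = 0.99. All of these inputs are assumptions.

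**The case against.** The opening sentence of SAP 6.1 can be read narrowly: it says which partial dates receive a handling rule, not that a complete stop date must be ignored. A careful programmer could fall back on the SAP 5.6 definition and exclude the event. That reading is possible, and it makes this a drafting gap rather than a deliberate choice. It does not remove the conflict. The three rules say without exception when an event is treatment emergent, and a programmer who follows them literally gets the wrong flag. The concomitant medication rules in the same appendix do classify by stop date, so a literal reader would take its absence from the adverse event rules as intended.

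The stronger objection is that almost no one is affected. Under Protocol 3.1 and 5.11, consent, baseline and first application all fall at Visit 1/Day 1, so a subject without a wash-out has almost no pre-dose window. Screen failures are not entered in the database (Protocol 5.14). Protocol 2.2 accepts an approximate onset date, and missing data are queried (Protocol 10.1), so incomplete start dates should be uncommon. An event that ended before dosing fits the not-related category in Protocol 7.2, so counts of drug-related events should not rise. All of this stands, and it limits the size of the problem.

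SAP 5.2, listed in the contents as covering dropouts and missing data, is wholly redacted, and text is blacked out within and after the safety section. A clause there could resolve the point. Nothing visible does.

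**Conclusion.** The point holds as a minor internal contradiction. For an incomplete start date that meets one of the three rules, SAP 6.1 counts an event as treatment emergent even when its recorded stop date is before the first dose, contrary to SAP 5.6. It rests on the visible text and on the existence of subjects who consent before Day 1 for a wash-out. The effect cannot be quantified, because arm sizes, wash-out lengths and SAP 5.2 are redacted and the frequency of partial dates is unknown. It is probably very small.

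Three stronger readings are tempting, and the documents support none of them:

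- A reader might infer that several subjects per arm would be misclassified. No document figure supports any count or percentage.
- A reader might infer that a year-only start date sweeps in a whole calendar year of events. Reporting starts at consent, so the window is still consent to first dose.
- A reader might infer that counting events of unknown timing is itself the fault. That default is conservative and reasonable. The gap is only the missing exception where the timing is known.

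The any-TEAE test is also not part of the equivalence or superiority criteria in SAP 5.5, so the efficacy conclusions are untouched.

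**What to change.** Add one clause to each of the three adverse event rules in SAP 6.1: *unless the stop date, or its known part, shows that the event ended before the date of the first dose, in which case it is not treatment emergent.* Keep the present default where the stop date is missing or does not settle the question. If the redacted SAP 5.2 already contains such a condition, a cross-reference from 6.1 is enough.

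The cost is one sentence in the SAP and one line in the derivation of the TEAE flag. The stop date is already collected, so no change to the case report form is needed. The change should be made before the blind is broken.

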6.2 Summary of Assessments

The schedule of visits and procedures to be conducted at each visit are summarized in the Schedule of Study Procedures.
